## **4.2.6 Secondary efficacy outcome variables**

### **4.2.6.1 Secondary analyses**

For each secondary efficacy variable described in Section 3.2, the objective is to determine the effect of benralizumab on the time course of change (onset and maintenance of effect).

FEV1 responder at each post-baseline visit will be defined as a subject with change from baseline  $\geq$  prespecified cutoffs as in Section 3.1, and analysed using a logistic regression model with repeated measures using generalized equation estimate method. The model will include treatment, region, visit and treatment group by visit interaction as fixed factors, and baseline FEV1 scores as a covariate. The variance-covariance matrix will be assumed to be unstructured.

The percent change from baseline at each timepoint for the eosinophils counts, change from baseline at each timepoint for Pre-BD FVC, ACQ-6 score, SGRQ score, and FeNO will be compared between benralizumab and placebo using an MMRM analysis described in the primary analysis above. The least squares mean for the difference in treatment groups using the interaction between visit and treatment group, its 95% CI, and the 2-sided p-values will be reported for each post-baseline visit.

As for the primary endpoint, the first post-baseline timepoint where the p-value for the mean difference between benralizumab and placebo is less than or equal to 0.05 from the repeated measures analysis will be used to determine time to onset of effect for each secondary parameter. The average over the mean differences between benralizumab and placebo based on the change from baseline (Visit 4) to Days 28 (Visit 8), 56 (Visit 9), and 84 (Visit 10) will be used to determine maintenance of effect. Contrasts will be used to obtain estimates of the average treatment differences over Days 28, 56, and 84.

Results will be presented in terms of LSMEANS, treatment differences in LSMEANS, 95% CIs of treatment differences, and p-values at each planned timepoint. To explore correlations between changes in eosinophil depletion and lung function, and correlations between changes in FeNO and lung function, the following analyses will be conducted, blood eosinophil data collected at Screening visit will be used in the analyses below to be consistent with the subgroup analysis of pre-BD FEV1 by baseline EOS categories:

- Analyses will be conducted on change from baseline versus baseline eosinophil count at Day 28 and Day 84 in pre-BD FEV1 using a moving average and MMRM approach. In this analysis, patients will be ordered by baseline eosinophil count and grouped by percentile into overlapping subgroups (0 – 40th, 10th – 50th, 20th – 60th, 30th – 70th, 40th – 80th, 50th - 90th, 60th – 100th). The MMRM model will be then applied to each subgroup to estimate the treatment difference at Day 28 and Day 84 separately and associated 95% CI for each percentile grouping.
- A scatterplot of observed change in pre-BD FEV1 at Day 28 and 84 versus baseline eosinophils at Day 28 and Day 84 will be prepared separately with locally weighted scatter plot smoothing curves (LOESS) and corresponding 95% CIs superimposed.
- Same kinds of MMRM and LOESS analyses will be performed using baseline FeNO data.
- If significant treatment effect is detected at timepoints earlier than Day 28, the same kinds of MMRM and LOESS analyses will also be performed at the earliest timepoint where significant treatment effect is detected.

A scatter plot with correlation coefficient will be provided for baseline FeNO and EOS count data to evaluate the association between baseline FeNO and EOS.

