2.2 Secondary objectives

Secondary objectives	Outcome measure
To determine time course of effect of benralizumab on blood eosinophils and correlate changes in eosinophil depletion with lung function	Change from baseline in blood eosinophils (from hematology) to end of treatment together with the correlation with lung function
To determine the effect of benralizumab on the time course of change and maintenance on lung function.	Change from baseline (Visit 4) in pre-BD FEV ₁ at all clinic visits compared to placebo Change from baseline (Visit 4) in pre-BD forced vital capacity (FVC) at all clinic visits compared to placebo
To determine the time course of the effect of benralizumab on asthma control metrics	Change from baseline (Visit 4) in Asthma Control Questionnaire-6 (ACQ-6) score at all post-baseline assessment timepoints
To determine the time course of effect of benralizumab on health related quality of life	Change from baseline (Visit 4) in St. George's Respiratory Questionnaire (SGRQ) score at all post-baseline assessment timepoints
To determine the effect of benralizumab on the time course of change in exhaled nitric oxide (FeNO)	Change from baseline in FeNO (ppb) compared to placebo to end of treatment (Visit 10)

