#### 1.1.2 Secondary objectives

Secondary Objectives	Outcome Measures
To determine time course of effect of benralizumab on blood eosinophils and correlate changes in eosinophil depletion with lung function.	Change from baseline in blood eosinophils (from hematology) to end of treatment together with the correlation with lung function
To determine the effect of benralizumab on the time course of change and maintenance on lung function.	
 
Change from baseline (Visit 4) in pre-BD FEV1 at all clinic visits compared to placebo
 
Percent of responders in pre-BD FEV1 by pre-specified cutoffs compared to placebo at all visits.
 
Change from baseline (Visit 4) in pre-BD forced vital capacity (FVC) at all clinic visits compared to placebo
 

To determine the time course of the effect of benralizumab on asthma control metrics	Change from baseline (Visit 4) in Asthma Control Questionnaire-6 (ACQ-6) score at all post-baseline assessment timepoints
To determine the time course of effect of benralizumab on health-related quality-of-life	Change from baseline (Visit 4) in St. George's Respiratory Questionnaire (SGRQ) score at all post-baseline assessment timepoints

Secondary Objectives	Outcome Measures
To determine the effect of benralizumab on the time course of change in exhaled nitric oxide (FeNO)	Change from baseline in FeNO (ppb) compared to placebo to end of treatment (Visit 10)

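### SAP 4.2.6.1 sets out to correlate changes in eosinophils and FeNO with lung function but fixes pre-treatment markers for every analysis, so the correlation part of the first secondary objective gets no result

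*SAP*

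**What the plan says.** **The objective.** Protocol 2.2 gives the outcome measure for the first secondary objective as "Change from baseline in blood eosinophils (from hematology) to end of treatment together with the correlation with lung function". SAP 1.1.2 keeps that outcome measure, and its objective is partly to "correlate changes in eosinophil depletion with lung function".

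**The stated purpose of the analyses.** The lead-in in SAP 4.2.6.1 reads "To explore correlations between changes in eosinophil depletion and lung function, and correlations between changes in FeNO and lung function".

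**The rule in the same sentence.** It goes on to say that "blood eosinophil data collected at Screening visit will be used in the analyses below to be consistent with the subgroup analysis" by baseline eosinophil category (SAP 4.2.5.3).

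**The analyses listed.**
- A moving-average MMRM in seven overlapping percentile groups of baseline eosinophil count: "The MMRM model will be then applied to each subgroup to estimate the treatment difference at Day 28 and Day 84 separately".
- A LOESS scatterplot of FEV1 change "versus baseline eosinophils at Day 28 and Day 84 will be prepared separately".
- A FeNO counterpart: "Same kinds of MMRM and LOESS analyses will be performed using baseline FeNO data".
- A repeat of these at the earliest significant visit, if one falls before Day 28.
- "A scatter plot with correlation coefficient will be provided for baseline FeNO and EOS count data".

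**What else exists.** SAP 3.2.2 defines absolute and percent eosinophil change from Visit 4 at each post-baseline visit. SAP 4.2.6.1 compares the percent change between arms by MMRM. Protocol 8.5.2.1 gives no method for the correlation.

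**The concern.** A correlation of changes asks whether patients whose eosinophils fell further also gained more FEV1. An analysis by pre-treatment count asks whether patients who started higher gained more, or gained more relative to placebo. The second question is about effect modification or prognosis. It is worth asking, but it is a different question.

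The lead-in announces the first question and its own rule directs the work to the second. This is more than missing detail: a programmer who follows the stated rule will use the wrong variable for the stated purpose. At stake is one named secondary outcome measure. It would have no result, and the study report could present baseline-marker output as if it supplied one.

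**Working it through.** The SAP states no figure to reproduce on this point. The check sets each announced item against the variable it would use.

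**1. Marker used by each analysis in SAP 4.2.6.1**

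| Analysis | Marker | Lung-function variable | Uses a change in the marker? |
|---|---|---|---|
| Moving-average MMRM, eosinophils | Screening count | FEV1 change | No |
| LOESS, eosinophils | Baseline; Screening count under the lead-in rule | FEV1 change | No |
| Moving-average MMRM, FeNO | Baseline FeNO | FEV1 change | No |
| LOESS, FeNO | Baseline FeNO | FEV1 change | No |
| Conditional earlier visit | As above | FEV1 change | No |
| Scatter plot with coefficient | Baseline FeNO against baseline eosinophils | None | No |

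**2. Count of outputs**
- Moving-average treatment differences: 7 percentile windows x 2 days x 2 markers = 28. With the conditional earlier visit: 7 x 3 x 2 = 42.
- LOESS plots: 2 days x 2 markers = 4. With the conditional visit: 3 x 2 = 6.
- Number using a change in eosinophils or FeNO: 0 in every case.

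**3. Is the pairing specified anywhere else?** Eosinophil change appears in SAP 3.2.2 as a definition and in SAP 4.2.6.1 as a between-arm comparison. Protocol 8.4.1.2 uses it for the treatment effect over time. SAP 4.2.5.3 uses the pre-treatment count to form subgroups. SAP 4.2.11 summarises eosinophil levels by antibody status. None of these sets eosinophil change against FEV1 or FVC change.

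**4. Can the Screening count stand in for the change?** Not on the SAP's own definitions. Change is measured from Visit 4, whereas Protocol 3.1 takes the screening eosinophil count at Visit 1, five weeks earlier. The SAP nowhere says that one is meant as a proxy for the other.

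**5. The LOESS bullet.** A baseline count has no Day 28 or Day 84 value, so the bullet cannot stand as worded. The lead-in rule and the parallel MMRM bullet, which ties the days to FEV1 change, both point to the Screening count as the likely meaning.

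**6. Are the data available?** Yes. Protocol Table 3 schedules eosinophil counts and pre-BD spirometry at the treatment visits, and the change variable is already defined.

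**The case against.** **The LOESS bullet may have lost some words.** If change from baseline in eosinophils was meant, it would supply part of the missing analysis. That is possible but the less likely reading, given the Screening rule. It is a reason to ask the sponsor to confirm the meaning, not a reason to treat the objective as covered.

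**The added display may say little.** Protocol 1.1 describes depletion below the level of detection within 24 hours in asthmatic subjects, so change on benralizumab may vary little apart from the starting count. Protocol 3.7.1 expects lower counts on active treatment than on placebo, so a placebo coefficient would largely describe spontaneous variation. Much of this stands, and it limits what the display can show. A reader might infer that the coefficient cannot be estimated, or that in the benralizumab arm it would only repeat the baseline association. The documents do not support either: they do not say how low counts will be reported or how complete depletion will be in this trial, and the rule in SAP 3.5.2 for values recorded with a less-than sign applies only unless otherwise specified.

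**No protocol method was changed.** This is correct. A reader might see an undeclared departure that belonged in SAP section 6. But Protocol 8.5.2.1 gives no correlation method and SAP 1.1.2 keeps the outcome measure, so this is a mismatch within the SAP.

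**It is only exploratory.** This is also correct, and it sets the severity. It does not settle the mislabelling, because the correlation is a named secondary outcome measure.

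**Conclusion.** The concern holds as a minor point. The correlation part of the first secondary objective has no matching analysis: 0 of 28 default moving-average differences and 0 of 4 default LOESS plots use a change in the marker, and the one coefficient planned involves no lung-function variable. The conclusion rests on the text alone and needs no assumption about the data, beyond reading the LOESS bullet under the lead-in's Screening rule.

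The consequence is limited. SAP 4.1 makes all p-values outside the primary analysis nominal, and the FEV1 average over Days 28, 56 and 84 that decides whether the study is positive is untouched. A reader might infer that the whole objective goes unanswered. It does not: the eosinophil time course is analysed by MMRM with an onset rule, alongside that of FEV1, which also serves the design purpose in Protocol 1.1.

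**What to change.** In SAP 4.2.6.1:

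1. **Scope and labels.** Limit the Screening-count rule to the baseline-marker analyses. Label the moving-average MMRM as treatment effect by baseline eosinophils or FeNO, and the LOESS plots as association of FEV1 change with the baseline marker.
2. **LOESS bullet.** Reword it so that the days attach to FEV1 change only, against the Screening count, once the sponsor has confirmed that meaning.
3. **The correlation.** Add one exploratory display, by arm, of eosinophil change from Visit 4 (absolute and percent, as in SAP 3.2.2) against pre-BD FEV1 change at the same visit, on the days already used, with a Spearman coefficient and 95% CI. Note only that near-complete depletion may limit the spread of change on benralizumab. If the sponsor does not want the display, state that the correlation of changes is not planned and that the baseline analyses do not answer it.
4. **FeNO.** Treat FeNO change in the same way, or delete it from the lead-in, which is the only place that names its correlation with lung function.

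**Cost.** Items 1 and 2 are wording. For eosinophils, item 3 adds 2 days x 2 arms x 2 scales = 8 descriptive coefficients, or 3 x 2 x 2 = 12 with the conditional earlier visit, from data already scheduled. The alternative in item 3 is one sentence, at the price of leaving this part of the objective openly unanswered. The downside of the display is a little more exploratory output, possibly of limited value in the benralizumab arm.

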The results of the Phase 2b study, MI-CP220 (Castro et al 2014) and the Phase 3 asthma exacerbation studies, SIROCCO (Bleeker et al 2016) and CALIMA (Fitzgerald et al 2016) were used as a basis for the sample sizing. From these studies, it is expected that around 115 patients per treatment arm (230 in total) will provide approximately 90% power for the primary endpoint pre-BD FEV1 with type I error controlled at a two-sided alpha level of 0.05 if the true average over the mean treatment differences (benralizumab – placebo) across Days 28 (Visit 8), 56 (Visit 9), and 84 (Visit 10) is 138 mL. The sample size will also be sufficient to have approximately 80% power for an average over the mean treatment difference of 120 mL. The assumed variability has a within-group standard deviation of 375 mL and within-patient correlation of 0.6. If the within-patient variability is reduced to 350 mL, the sample size would be sufficient 80% power for an average of 110 mL. In addition, it is expected that around 115 patients per treatment arm will have 80% power to detect a true treatment difference (benralizumab – placebo) of 130 mL, assuming a within-group standard deviation of 350 mL or a true treatment difference of 140 mL, assuming a standard deviation of 375 mL. Based on these assumptions, the minimum difference that would be statistically significant at the 5% level ranges from approximately 85 to 100 mL. The sample size was estimated using nQuery + nTerim version 3.0 using methodology by Liu et al (Liu et al 2005).

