## **4. ANALYSIS METHODS**

### **4.1 General principles**

The analysis of the primary and secondary efficacy endpoints will include all data captured during the 12-week double-blind treatment period, defined as the period after administration of randomized IP at Visit 4 (Week 0) and the conclusion of Visit 10 (Week 12), inclusive. This includes data regardless of whether study treatment was prematurely discontinued or delayed, and/or irrespective of protocol adherence, unless the patient withdraws consent to study participation. The statistical analyses will compare benralizumab with placebo. The analysis of safety endpoints will include all data captured during the on-study period, defined as the period after first administration of randomized IP at Visit 4 (Week 0) and the conclusion of the scheduled post-treatment FU visit (Week 11), inclusive.

The data analyses will be conducted using the SAS® System 9.2 (SAS Institute Inc., Cary, NC) or higher version. Pharmacokinetic analyses will be performed using WinNonlin (version 6.3, or higher, Certara, L.P., St. Louis, MO).

Summary data will be presented in tabular format by treatment group. Descriptive statistics on continuous variables will be summarized by treatment group using mean, standard deviation, median, quartile, and range as applicable, while categorical data will be summarized using frequency counts and percentages. When data are summarized by time, the values recorded against the scheduled timepoints listed in the protocol will be used. When assessing minimum/maximum increases or decreases during the study, all assessments, including unscheduled assessments will be used. For analysis assessing change from baseline, only patients with both baseline and at least 1 evaluable post-baseline measure will be included.

Given there is a single primary endpoint and treatment comparison, no formal testing strategy will be used for the analysis in this study.

All hypothesis testing will be reported using 2-sided tests. All p-values apart from the primary analyses of the primary endpoint will be nominal. All p-values will be rounded to 4 decimal places.

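### The early FEV1 analyses by baseline eosinophils and FeNO run only at the first significant visit before Day 28, so the treatment differences they show are selected upward and they may not be run at all

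*SAP*

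**What the plan says.** SAP 4.2.6.1 orders patients by baseline eosinophil count, forms seven overlapping windows that each hold 40% of patients, and estimates the treatment difference in pre-BD FEV1 in each window by MMRM, with a 95% CI, at Days 28 and 84. LOESS plots accompany these, and the whole set is repeated for baseline FeNO.

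For earlier visits the section adds a condition: "If significant treatment effect is detected at timepoints earlier than Day 28, the same kinds of MMRM and LOESS analyses will also be performed". Only one such visit is then analysed, namely the first to qualify. The visits concerned are Days 3, 7 and 14. The section does not say which outcome or model defines significance. The natural reading is the onset rule of SAP 1.1.1 and 4.2.5.1, which is an overall p-value of 0.05 or less at a visit in the primary MMRM, unadjusted across visits.

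Two other passages bear on this. SAP 4.2.5.3 commits, without any such condition, to a subgroup analysis of pre-BD FEV1 by eosinophils (300-449 and 450 or more per µL) and FeNO (up to 50 and above 50 ppb). It names no visits, and it calls the subgroup analyses exploratory. SAP 4.1 states: "All p-values apart from the primary analyses of the primary endpoint will be nominal".

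**The concern.** Protocol 1.1 gives the purpose of the study as describing when lung function changes relative to the depletion of blood eosinophils, which it reports as maximal within 24 hours in asthmatic subjects. The visits in the first two weeks are therefore central, and they are the ones where the marker analyses depend on the data.

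The rule has two consequences.

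- **Selection of level.** The window estimates come from the same FEV1 values that had to cross the significance threshold, at a visit chosen because it crossed first. Their treatment differences are too high on average, and the intervals make no allowance for it.
- **Conditional omission.** If only patients with high marker values respond early, the overall difference is diluted. The condition then tends to fail in the situation where the marker plots would be most informative.

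At stake is the reading of exploratory early curves that serve a stated secondary objective. The primary conclusion is not at stake.

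**Working it through.** **Inputs from SAP 1.3.** 115 per arm; two-sided 0.05 ("type I error controlled at a two-sided alpha level of 0.05"); variability as in "The assumed variability has a within-group standard deviation of 375 mL and within-patient correlation of 0.6".

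**Assumptions not in the documents.** Effects at Days 3, 7 and 14; the SD at those visits (375 mL, with 250 mL as an alternative); the same correlation at early visits; no missing data; significance judged on the overall primary MMRM.

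**Step 1: the plan's own figures.** The SD of a three-visit average is 375 × √((1 + 2 × 0.6)/3) = 321 mL. Its SE is 321 × √(2/115) = 42.3 mL. Power for 138 mL is Φ(138/42.3 − 1.96) = 90.3%, against a stated 90%. For 120 mL it is 80.9%, against a stated 80%. For 110 mL at SD 350 mL it is 79.5%, against a stated 80%. The plan's figures reproduce.

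**Step 2: threshold at one early visit.** SE = 375 × √(2/115) = 49.5 mL, so an overall difference of about 1.96 × 49.5 = 97 mL is needed.

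**Step 3: how selection passes to a window.** A 40% window holds 0.4 × 115 = 46 per arm. Let W be its estimate, R the estimate in the other 60%, and O = 0.4W + 0.6R. Then cov(W, O) = 0.4 × 2σ²/46 = 2σ²/115 = var(O), so the regression of W on O has slope 1. Selecting on O therefore moves every window by the same expected amount, and differences between windows are unchanged.

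**Step 4: simulation.** Differences at Days 3, 7 and 14 are drawn as correlated normals (0.6), and the first visit with p ≤ 0.05 is selected. With the same true difference at all three visits and in all patients, counting triggers that favour benralizumab:

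| SD | True difference | Condition met | Mean at selected visit |
|---|---|---|---|
| 375 mL | 50 mL | 32% | 120 mL |
| 375 mL | 80 mL | 58% | 127 mL |
| 375 mL | 138 mL | 93% | 152 mL |
| 375 mL | 200 mL | 99.8% | 201 mL |
| 250 mL | 80 mL | 87% | 94 mL |
| 250 mL | 138 mL | 99.9% | 139 mL |

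With no early effect the condition is met in 12% of trials, counting both directions. About half of those favour placebo.

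**Step 5: effect confined to the top 40% by marker.** A difference of 150 mL there and 0 elsewhere gives 0.4 × 150 = 60 mL overall.

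- SD 375 mL: not run in 59% of trials (57 to 65% for correlation 0.5 to 0.8). When run, the overall difference averages 121 mL, a shift of 121 − 60 = 61 mL. The top 40% show about 150 + 61 = 211 mL and the rest about 61 mL instead of 0. The contrast is 211 − 61 = 150 mL, as it should be.
- SD 250 mL: not run in 30 to 40% over the same correlations. When run, the shift is about 86 − 60 = 26 mL.
- Other sizes at SD 375 mL: not run in 63% for 138 mL, 42% for 200 mL and 13% for 300 mL.

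**Step 6: precision of one window.** SE = 375 × √(2/46) = 78 mL, so the 95% half-width is 1.96 × 78 = 153 mL.

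**The case against.** The strongest case on the other side has four parts.

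1. **The markers are examined elsewhere.** A reader might infer that SAP 4.2.6.1 is the only planned look at these markers, so that an early marker-dependent effect would never be examined. The documents do not support that, because SAP 4.2.5.3 has an unconditional subgroup analysis by both. What remains is that it names no visits, and the general subgroup list in the same section is tied to maintenance of effect. It does not guarantee an early estimate.
2. **The relationship of interest is not biased.** A reader might infer that the rule distorts the association between marker and response. It does not: by step 3 the high-versus-low contrast is preserved. But the SAP reports a treatment difference and CI for each window, and those levels are affected. In step 5 a group with no response appears to gain about 61 mL.
3. **The size depends on assumed effects.** This stands. Inflation is about 10% at 138 mL overall with SD 375 mL, and under 1% at 200 mL. Omission is a minority outcome at SD 250 mL, or with a 300 mL subgroup effect. The omission scenario also assumes no early effect in the lower 60%, although every patient must have at least 300 cells/µL.
4. **The analyses are exploratory and imprecise.** Also true. Limiting output is a defensible aim, and SAP 4.2.5.1 shows the unselected overall difference at every visit. But nominal status does not remove estimation bias. It does remove any multiplicity reason for making the analyses conditional on significance.

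**Conclusion.** The point holds in a limited form. The rule makes the only marker analyses explicitly specified at an early visit conditional on the data. When they run, it raises the treatment difference in every window by about the same amount, with intervals that ignore this. At SD 375 mL and correlation 0.6 the shift is about 47 mL for a true 80 mL (127 − 80) and 14 mL for a true 138 mL (152 − 138). At SD 250 mL it is about 14 mL for 80 mL (94 − 80) and negligible for 138 mL. With 150 mL confined to the top 40% by marker, the early analyses are omitted in about 59% of trials at SD 375 mL and 30 to 40% at SD 250 mL.

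These sizes rest on assumed early effects and SDs, complete data, and the overall onset rule as the meaning of significant. The MMRM window estimates were simulated; the LOESS plots were not, though they use the same selected visit.

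The primary result, the onset determination, the overall estimates by visit and the contrast between marker windows are all unaffected. This is an inexpensive improvement to an exploratory analysis, not a flaw in the trial's main inference.

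**What to change.** Replace the conditional bullet in SAP 4.2.6.1 with:

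*The same MMRM and LOESS analyses will be performed at Days 3, 7 and 14, irrespective of the significance of the overall treatment difference at those visits.*

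The analyses then always run, and the selection bias disappears because no visit is chosen by its result.

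The cost is one SAP sentence and further runs of planned programs. If the window models have the same form as the primary MMRM, the early contrasts come from fits already planned for Days 28 and 84. The downside is more exploratory output: 3 visits × 2 markers × 7 windows = 42 early window estimates plus the LOESS plots. Each is imprecise at about 46 patients per arm.
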